Hematological and chemistry laboratory parameters will be graded according to the NCI-CTCAE V5.0 where applicable. The worst severity grade, time to maximum Grade 3 or 4 value, and time to resolution (return to baseline grade or below) will be summarized.

Safety data (AEs and clinical laboratory results) will be summarized descriptively. A list of 12-lead electrocardiogram findings will be presented by patient.

[figure not shown]
Population PK and Exposure-Response Analyses

PK data will be pooled with data from other studies for a popPK analysis. The relationship between popPK model derived exposure and response will be explored for each cohort. The popPK and Exposure-Response (E-R) analyses will be described in a separate popPK/E-R Analysis Plan.

Pharmacodynamic Analyses

Pharmacodynamic and biomarker data will be summarized descriptively using all patients in the Pharmacodynamic/Biomarker Evaluable Set who have evaluable data available.

Study Schema

Schedule of Events

Evaluations on Day 1 (D1) of a cycle should be performed within 24 hours prior to dosing, unless otherwise noted. Procedures already performed during the screening period within 72 hours prior to dosing do not need to be repeated on Cycle 1 Day 1 (C1D1). The first study drug administration will occur on C1D1. The End of Treatment (EOT) visit must be performed within 7 days after a decision is made to discontinue study drug (for patients who discontinue at a planned study visit, that visit may be considered the EOT visit if all assessments required at EOT are performed). Required assessments for patients in Cohorts A and B are presented in [Table 1](#) and for Cohort C in [Table 2](#). Required assessments during the Study Extension phase are presented in [Table 3](#) for all cohorts.

Table 1: Schedule of Events (Cohorts A and B)

Evaluation	Screening (Within 28 days of 1 st dose)	Treatment Period (1 cycle =28 days)						End of Treatment (+7 days)	Safety Follow-up 30 days after last dose (+7 days)	Survival Follow-up Period (every 12±2 weeks)	Notes				
		Cycle 1				Cycle ≥2									
		D1 (±3 days)	D8 (±3 days)	D15 (±3 days)	D22 (±3 days)	D1 (±3 days)	End of Cycle (±7 days)								
Documented informed consent	X										Documented informed consent will be obtained prior to any study-related assessments or procedures.				
Review eligibility criteria	X														
Demographics/medical history	X														
Review of baseline signs and symptoms	X														

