Prior & concomitant medications, AE assessments		→													
Physical examination	X	X				X		X	X		Within 24 hours prior to dosing.				
Vital signs	X	X				X		X	X		Heart rate, blood pressure, body temperature, and respiration rate.				
Height and weight	X	X				X		X	X		Height at screening only.				
ECOG performance status	X	X				X		X	X		Within 24 hours prior to dosing.				
12-Lead electrocardiogram	X	X				X		X	X						
Hematology	X	X	X	X	X	X		X	X		Within 24 hours prior to dosing. More frequent assessments may be performed if clinically indicated				
Coagulation	X	X				X		X	X		Within 24 hours prior to dosing.				
Chemistry (serum or plasma)	X	X	X	X	X	X		X	X		Within 24 hours prior to dosing.				

Evaluation	Screening (Within 28 days of 1 st dose)	Treatment Period (1 cycle =28 days)						Notes	
		Cycle 1			Cycle ≥2				
		D1 (±3 days)	D8 (±3 days)	D15 (±3 days)	D22 (±3 days)	D1 (±3 days)	End of Cycle (±7 days)		
Pregnancy test	X Within 7 days						X		Serum pregnancy test required for WOCBP. Additional testing may be required by local regulations.
Ophthalmological examination	X			See Note					Examination to be performed by an ophthalmologist or qualified delegate at screening, 4-6 weeks after first dose, and as indicated if symptoms or signs of mineral deposits.
PK blood sampling				See Note					Pre-dose (from -30 min to just before dose), 1 h±30 min post-dose, and 3 h±30 min post-dose
ctDNA blood samples	X						X		
Tumor tissue sample	X								Archival or fresh tumor biopsy
Response assessments (CT/MRI)	X						X	X	At baseline and the end of every 2 cycles ±7 days), or as clinically indicated, until radiologic PD or initiation of new anticancer therapy (whichever comes first). For patients who discontinue treatment for reasons other than radiographic disease progression, imaging will be performed at EOT, (if the prior scan was performed ≥9 weeks) and during Survival Follow-up until radiologic disease progression or initiation of new anticancer therapy (whichever occurs first) unless patient withdraws consent.
Survival status								X	For all patients, unless patient withdraws consent or the study is terminated early by the Sponsor.

Table 2: Schedule of Events (Cohort C)

Evaluation	Screening (Within 28 days of 1 st dose)	Treatment Period (1 cycle =28 days)						End of Treatment (+7 days)	Safety Follow-up 30 days after last dose (+7 days)	Survival Follow-up Period (every 12±2 weeks)	Notes				
		Cycle 1				Cycle ≥2									

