Pregnancy test	X Within 7 days					
Ophthalmological examination	X		See Note			
PK blood sampling			See Note			
ctDNA blood samples	X					
Tumor tissue sample	X					
Tumor assessments (CT/MRI)	X					
Survival status						

Screening
(Within 28 days of 1st dose)

Safety Follow-up
(± 7 days)

Survival Follow-up
(every 12 ± 2 weeks)

Notes

Serum pregnancy test required for WOCBP. Additional testing may be required by local regulations.

Examination to be performed by an ophthalmologist or qualified delegate at screening, 4-6 weeks after first dose, and as indicated if symptoms or signs of mineral deposits.

Pre-dose (from -30 min to just before dose), 1 h \pm 30 min post-dose, and 3 h \pm 30 min post-dose

Archival or fresh tumor biopsy

At baseline and the end of every 2 cycles \pm 7 days), or as clinically indicated, until radiologic PD or initiation of new anticancer therapy (whichever comes first).

For patients who discontinue treatment for reasons other than radiographic disease progression, imaging will be performed at EOT, (if the prior scan was performed ≥ 9 weeks) and during Survival Follow-up until radiologic disease progression or initiation of new anticancer therapy (whichever occurs first) unless patient withdraws consent.

For all patients, unless patient withdraws consent or the study is terminated early by the Sponsor.

Table 2. Schedule of Events (Cohort C)

Evaluation	Treatment Period (1 cycle =28 days)				Notes
	Cycle 1	Cycle ≥2	End of Cycle (±7 days)	End of Treatment (±7 days)	
Written informed consent					Written informed consent will be obtained prior to any study-related assessments or procedures.
Review eligibility criteria	X				
Demographics/medical history	X				
Review of baseline signs and symptoms	X				
Prior & concomitant medications, AE assessments					
Physical examination	X	X	X	X	Within 24 hours prior to dosing
Vital signs	X	X	X	X	Heart rate, blood pressure, body temperature, and respiration rate.
Height and weight	X	X	X	X	Height at screening only.
ECOG performance status	X	X	X	X	Within 24 hours prior to dosing
12-Lead electrocardiogram	X	X	X	X	
Hematology	X	X	X	X	Within 24 hours prior to dosing More frequent assessments may be performed if clinically indicated
Coagulation	X	X	X	X	Within 24 hours prior to dosing
Chemistry (serum or plasma)	X	X	X	X	Within 24 hours prior to dosing
Pregnancy test	X	Within 7 days		X	Serum pregnancy test required for WOCBP. Additional testing may be required by local regulations.

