4	Treatment discontinuation for reasons other than PD or death, and no post baseline tumor assessments	Date of the first dose	Censored
5	Treatment discontinuation for reasons other than PD or death with post baseline tumor assessments	Date of the last tumor assessment	Censored
6	New anticancer treatment started	Date of the last tumor assessment before start of new treatment	Censored
7	Death or PD after two or more missed tumor assessments ^c	Date of the last tumor assessment before missed assessments	Censored
8	No baseline or unreadable baseline assessment but readable post baseline assessments	Date of the first dose	Censored

^a This refers to patients who were still receiving study treatment at time of data cutoff.

^b For PFS analysis, the date of last tumor assessment refers to the date of last adequate tumor assessment.

^c Two or more missed tumor assessments is defined as having either one of the following two durations being longer than 126 days (= (28 [days/cycle] x 2 [cycles] + 7 [days]) x 2):

Duration between two consecutive tumor assessments

Duration between the last tumor assessment and death or PD

Table 11: Censoring Rules for Overall Survival (OS)

No.	Situation	End Date
1	Death before cut-off	Date of death
2	Death after data cut-off	Date of data cut-off
3	Patient still alive at data cut-off	Date of data cut-off
5	Patient discontinued treatment due to any reason before data cut-off	Date last known to be alive

Table 12: Censoring Rules for Duration of Response (DOR)

No.	Situation	End Date	Outcome
1	Documented PD between scheduled visits	Date of the first assessment that determined PD	DOR event
2	Death during the study with no prior PD	Date of death	DOR event
3	Patients still on treatment without PD as of data cut-off ^a	Date of the last tumor assessment ^b	Censored
4	Treatment discontinuation for reasons other than PD or death	Date of the last tumor assessment	Censored

No.	Situation	End Date	Outcome
5	New anticancer treatment started	Date of the last tumor assessment before start of new treatment	Censored
6	Death or PD after two or more missed tumor assessments ^c	Date of the last tumor assessment before missed assessments	Censored

^a This refers to patients who were still receiving study treatment at time of data cutoff.

^b For DOR, the date of last tumor assessment refers to the date of last adequate tumor assessment.

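### The SAP's 126-day missed-scan rule does not exempt the baseline scan, so one missed first scan can count as two and a documented progression be censored before first dose

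*SAP*

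**What the plan says.** SAP Section 5.5.1.2, Table 10, row 7, censors a death or progression that comes after two or more missed tumor assessments. The end date is the "Date of the last tumor assessment before missed assessments". Footnote c replaces a count of missed visits with a duration: "Two or more missed tumor assessments is defined as having either one of the following two durations being longer than 126 days". The two durations are "Duration between two consecutive tumor assessments" and "Duration between the last tumor assessment and death or PD". Neither carries a post-baseline qualifier, although rows 4, 5 and 8 of the same table do.

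The SAP schedule (Section 3.1, Table 1) lists the screening scan in its tumor assessment row, and screening may begin 28 days before first dose. Protocol Table 1 sets the imaging times as "At baseline and the end of every 2 cycles ±7 days), or as clinically indicated". PFS starts at first dose.

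For deaths, Table 10 row 2 counts a death without prior progression as an event. The text of Section 5.5.1.2 censors at first dose every patient with no post-baseline assessment. Protocol Section 11.5.3.1.2 limits that first-dose rule to patients who did not die, and it has no missed-scan rule.

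SAP Section 5.5.2.2 applies Table 10 to PFS in Cohort C as well. Table 17 (EFS) repeats the 126-day definition for response assessments.

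**The concern.** The 126 days are built from two on-study scan intervals. On-study scans are timed from first dose, but the baseline scan is timed by screening. The interval from baseline to the first on-study scan can therefore run 28 days longer than the formula provides for.

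A patient who missed one scan can then meet a definition meant for two. If that patient's progression is documented at the next scheduled scan, row 7 removes it and sets the end date at the baseline scan, before the PFS clock starts. Whether this happens depends on how early the screening scan was booked, which has nothing to do with the patient's outcome. The SAP does not say how a negative PFS time is to be handled.

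**Working it through.** **Inputs**
- Cycle length 28 days, scans every 2 cycles, window ±7 days (Protocol Table 1).
- Baseline scan 0 to 28 days before first dose (same table).
- Threshold: more than 126 days (SAP Table 10, footnote c).
- Nominal on-study scans at days 56, 112, 168 and 224 after first dose.

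**The plan's own figure.** (28 × 2 + 7) × 2 = 63 × 2 = 126. It reproduces exactly.

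**Between on-study scans the rule works**
- One missed: 2 × 56 ± 14 = 98 to 126 days, never above 126.
- Two missed: 3 × 56 ± 14 = 154 to 182 days, always above 126.

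**From the baseline scan it does not.** Let b be the days from baseline scan to first dose.
- None missed: the longest gap is 28 + 63 = 91 days.
- Week-8 scan missed, progression at the second scan: b + 112 ± 7, so 0 + 105 = 105 to 28 + 119 = 147 days.
- First two scans missed: b + 168 ± 7, so 161 to 203 days.

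The one-miss range crosses the threshold when b exceeds 126 minus the scan day:

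| Second scan on day | Misclassified if baseline was more than |
|---|---|
| 105 | 21 days before first dose |
| 112 | 14 days before first dose |
| 119 | 7 days before first dose |

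**Example.** Baseline scan 27 days before first dose, week-8 scan missed, progression at day 112. The gap is 27 + 112 = 139 days, above 126. Row 7 moves the end date to the baseline scan, so the PFS time is about −27 days, with one scan missed.

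**Share misclassified among such patients (illustration).** The documents do not give baseline-scan timing, so it is assumed here, with every day in the ±7 window equally likely.
- Baseline uniform over 1 to 28 days before dose: 210 of 420 combinations exceed 126, or 50% (48% if day 0 is included).
- Uniform over 1 to 14 days: 28 of 210, or 13%.
- All within 7 days: none, since 7 + 119 = 126.

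**Deaths with no post-baseline scan.** With b = 28, the gap passes 126 from day 126 − 28 + 1 = 99, when only the week-8 scan has been missed. Three rules then apply: row 2 gives an event, row 7 gives censoring at the baseline scan, and the section text gives censoring at first dose.

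**Direction of the effect.** Take N patients, no other censoring, and D events by time t.
- Before the removed event, the curve falls from 1 − D/N to 1 − D/(N − 1), slightly lower.
- From that event onward, 1 − D/N becomes 1 − (D − 1)/(N − 1), which is higher whenever D < N.

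**Check of the remedy.** Measured from first dose, one missed scan gives 112 ± 7 = 105 to 119 days, never above 126. Two missed give 168 ± 7 = 161 to 175, always above. Counting the end of Cycle 2 as 55 days after first dose shifts gaps from baseline or first dose by one day and changes no conclusion.

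**The case against.** The SAP never states that the gap starts at the baseline scan. Its formula uses only on-study intervals, which suggests that on-study scans were intended. That may well be so, but footnote c is unqualified where neighbouring rows are qualified, and the schedule counts the baseline scan as a tumor assessment. A programmer following the text would include it. The sentence that censors at first dose does not rescue the progression case either, because the scan that shows progression is itself a post-baseline assessment.

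The objection does stand against three stronger readings that a reader might infer.
- **Early deaths are also censored before Day 1.** The documents do not settle this. For a death with no post-baseline scan, two other rules give a different answer, so the finding there is a conflict between rules.
- **A count of affected patients, such as a few per 100 in Cohort A.** Any such count needs the joint frequency of a missed week-8 scan and progression near week 16, plus baseline-scan timing. Neither is given. Scans done when clinically indicated, and the end-of-treatment scan required when the last one is at least 9 weeks old and treatment stopped without radiographic progression, would also shorten some gaps.
- **PFS is biased upward throughout.** The curve is raised only from the time of the removed event. Before it, the curve is slightly lower. The documents give no expected PFS, so the effect on the median cannot be signed.

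It is also fair that PFS is a secondary endpoint, estimated without a comparator.

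**Conclusion.** Wrong as written, of minor severity. On the literal text, one missed scan can be scored as two, and a documented progression can be censored before first dose. This arises only when the first on-study scan is missed and the baseline scan was more than 7 to 21 days before first dose, depending on the day of the second scan. Among patients who miss only that scan and progress at the next, the share affected runs from none to about half under the timing assumptions shown. The number of patients is unknown.

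Where it occurs, a true event is lost and the PFS curve is raised from that time onward. Cohort C, planned at about 20 patients, uses the same table, so a single lost event would weigh more there. The primary ORR analysis does not use this rule. DOR starts at first response, after the baseline interval, so it does not share this problem.

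The treatment of deaths with no post-baseline scan is a separate inconsistency within the SAP and needs to be reconciled.

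**What to change.** 1. Table 10, footnote c (PFS in Cohorts A, B and C): add that the interval before the first post-baseline assessment is measured from the date of first dose.
2. Table 10, row 7: set the end date to the later of first dose and the last adequate assessment before the missed assessments.
3. Section 5.5.1.2 and Table 10: state which of row 2, row 7 and the first-dose sentence takes precedence when a patient dies with no post-baseline scan, and reconcile this with the protocol, whose first-dose rule excludes deaths. Carry the same wording into Section 5.5.2.2 for Cohort C.
4. Table 17, footnote c (EFS): apply the same first-dose anchor. EFS also starts at first dose. For patients without a CR, row 13 censors at last contact, so a negative time does not arise there, but one missed assessment can still be counted as two.

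The cost is a few sentences in the SAP and one programming condition. No new data are needed, and the 126-day limit and the ORR analysis stay as they are.

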5.5.2. Cohort C

The description of each efficacy endpoint for Cohort C is provided in [Table 13](#) .

Table 13: Efficacy Endpoint Definitions for Cohort C

Endpoint	Definition
CR rate	The proportion of patients who achieved a CR per the Response Definition (Table 14)
ORR	The proportion of patients who achieved a CR, CRi, or PR
CR+CRi rate	The proportion of patients who achieved a CR or CRi
CCyR rate	The proportion of patients who achieved CCyR
PCyR rate	The proportion of patients who achieved PCyR
Duration of CR	The time from the first documentation of CR to the first documentation of objective tumor progression or death due to any cause, whichever occurs first
Duration of CR+CRi	The time from the first documentation of CR or CRi to the first documentation of objective tumor progression or death due to any cause, whichever occurs first
DOR	The time from the first documentation of CR, CRi, or PR to the first documentation of objective tumor progression or death due to any cause, whichever occurs first
PFS	The time from first dose of study therapy to the date of death (any cause) or disease progression, whichever occurs first
RFS	The time from the first documentation of CR to the first documentation of disease relapse or death due to any cause, whichever occurs first
EFS	The time from first dose of study therapy to treatment failure (defined as PD in this study), disease relapse after CR, or patient death from any cause
OS	The time from the date of first dose to the death date

5.5.2.1. Primary Efficacy Analysis

CR rate will be calculated and the 2-sided 95% CI will be derived by Clopper–Pearson method.

The confirmation of the best objective response of CR with at least 4 weeks interval of two consecutive time points is not required; however, CR must be confirmed by a minimum of 2 bone marrow assessments when the first response assessment shows marrow fibrosis. If applicable, responses recorded after disease progression or initiation of new anticancer treatment will be excluded.

Response will be determined based on disease presentation, and Investigators will assess response based on the Response Definition described in [Table 14](#). All the response assessments by Investigators will be adjudicated by a response adjudication committee.

Table 14: Response Definitions for Cohort C

MLN Characteristic	MLN Only	Lymphoma Presentation	Leukemia Presentation
Response Criteria	Savona 2015 ^a	Younes 2017 ^b	Cheson 2003 ^c
Complete response (CR)	Must fulfill all criteria defined for CR	Must fulfill all criteria defined for CR	Must fulfill all criteria defined for morphologic complete response CR does not include: 
 • morphologic leukemia-free state • complete response with incomplete hematological recovery (CRi), or cytologic complete response (CRc)
Partial response (PR)	Must fulfill all criteria defined for PR	Must fulfill all criteria defined for PR	Must fulfill all criteria defined for partial remission
Complete response with incomplete blood count recovery (CRi)	N/A	N/A	Must fulfill all criteria defined for CRi
Complete cytogenetic response (CCyR)	Resolution of previously present chromosomal abnormality known to be associated with MLN (eg. 8p11 translocation)	Must fulfill all criteria defined for CCyR	Must fulfill all criteria defined for cytogenetic complete response (CRc) and CCyR

^a Savona, et al. An international consortium proposal of uniform response criteria for myelodysplastic/myeloproliferative neoplasms (MDS/MPN) in adults. *Blood*. 2015.

^b Younes, et al. International Working Group consensus response evaluation criteria in lymphoma (RECIL 2017). *Ann Oncol*. 2017.

^c Cheson, et al. Revised recommendations of the International Working Group for Diagnosis, Standardization of Response Criteria, Treatment Outcomes, and Reporting Standards for Therapeutic Trials in Acute Myeloid Leukemia. *J Clin Oncol*. 2003.

5.5.2.2. Secondary Efficacy Analyses

- ORR, CR+CRi rate (if applicable in leukemia presentation), CCyR rate, and PCyR rate will be calculated and the 2-sided 95% CI will be derived by Clopper–Pearson method. Note that the ORR in Cohort C is defined as the proportion of patients who achieved a CR, CRi, or PR.
- PFS will be estimated using the Kaplan–Meier method. Patients who did not progress or die will be censored on the date of their last response assessment. Patients who did not have any post-baseline assessments will be censored on the first dosing date. Patients who started any subsequent anti-cancer therapy without a prior reported progression will be censored at the last response assessment prior to initiation of the subsequent anti-cancer therapy. The censoring rule for PFS is in [Table 10](#).
- Overall survival will be estimated using the Kaplan–Meier method. In the absence of confirmation of death or for patients who are alive as of the OS cut-off date, survival time will be censored at the last known date that the patient was alive. The censoring rule for OS is in [Table 11](#).
- DOR will be evaluated only in patients with an objective response of CR, PR, or CRi (if applicable in leukemia presentation). Duration of CR will be evaluated only in patients with an objective response of CR. Duration of CR+CRi will be evaluated only in patients with an objective response of CR or CRi (if applicable in leukemia presentation). DOR is defined as the time from the first documentation of CR, CRi, or PR to the first documentation of objective tumor progression or death due to any cause, whichever occurs first. Duration of CR (CR+CRi) is defined as the time from the first documentation of CR (CR or CRi) to the first documentation of objective tumor progression or death due to any cause, whichever occurs first. DOR, duration of CR, and duration of CR+CRi will be estimated using the Kaplan–Meier method. Patients who are alive and progression/relapse-free as of the data cut-off date will be censored at their last evaluable tumor response assessment prior to initiation of any new anticancer treatment. Patients who start subsequent anticancer therapy without a prior reported progression/relapse will be censored at the last response assessments prior to initiation of the subsequent anticancer therapy. The censoring rule for DOR is in [Table 12](#), and that for duration of CR and for duration of CR+CRi is in [Table 15](#).
- RFS will be evaluated only in patients with an objective response of CR. RFS will be estimated using the Kaplan–Meier method. RFS is measured from the first date of achieving CR until the first date of disease relapse or death from any cause, whichever occurs first. Patients who die without a reported disease relapse will be considered to have relapsed on the date of their death. Patients who did not relapse or die will be censored on the date of their last response assessment. Patients who started any subsequent anti-cancer therapy without a prior reported relapse will be censored at the last response assessment prior to initiation of the subsequent anti-cancer therapy. The censoring rule for RFS is in [Table 16](#).
- EFS will be estimated only in patients with leukemia presentation. EFS will be estimated using the Kaplan–Meier method. EFS is defined as the time from the first dose of study therapy to treatment failure, relapse after CR (if applicable), or death

from any cause, whichever occurs first. Treatment failure for EFS is defined as PD in this study. If the patient does not achieve a CR, EFS is defined as the point of treatment failure (PD) or death, whichever comes first. For a patient with none of these events before the end of the study follow-up, observation of EFS is censored at the date of the last contact prior to the analysis cut-off date. The censoring rule for EFS is described in [Table 17](#). Note that the start date of EFS is the same regardless of achieving a CR.

Table 15: Censoring Rules for Duration of CR and Duration of CR+CRi

No.	Situation	End Date	Outcome
1	Disease relapse between scheduled visits	Date of the first assessment that determined disease relapse	Event
2	Death during the study with no prior disease relapse	Date of death	Event
3	Patients still on treatment without disease relapse as of data cut-off ^a	Date of the last response assessment ^b	Censored
4	Treatment discontinuation for reasons other than disease relapse or death	Date of the last response assessment	Censored
5	New anticancer treatment started	Date of the last response assessment before start of new treatment	Censored
6	Death or disease relapse after two or more missed response assessments ^c	Date of the last response assessment before missed assessments	Censored

^aThis refers to patients who were still receiving study treatment at time of data cutoff.

^bFor duration of CR and duration of CR+CRi, the date of last response assessment refers to the date of last adequate response assessment.

^cTwo or more missed response assessments is defined as having either one of the following two durations being longer than 126 days (= (28 [days/cycle] x 2 [cycles] + 7 [days]) x 2):

Duration between two consecutive response assessments

Duration between the last response assessment and death or disease relapse

Table 16: Censoring Rules for Relapse-free Survival (RFS)

No.	Situation	Event or Censoring Date	Outcome
1	Disease relapse between scheduled visits	Date of the first assessment that determined disease relapse	Event
2	Death during the study with no prior disease relapse	Date of death	Event
3	Patients still on treatment without disease relapse as of data cut-off ^a	Date of the last response assessment ^b	Censored
4	Treatment discontinuation for reasons other than disease relapse or death	Date of the last response assessment	Censored
5	New anticancer treatment started	Date of the last response assessment before start of new treatment	Censored
6	Death or disease relapse after two or more missed response assessments ^c	Date of the last response assessment before start of new treatment	Censored

^a This refers to patients who were still receiving study treatment at time of data cutoff.

^b For RFS, the date of last response assessment refers to the date of last adequate response assessment.

^cTwo or more missed response assessments is defined as having either one of the following two durations being longer than 126 days (= (28 [days/cycle] x 2 [cycles] + 7 [days]) x 2):

Duration between two consecutive response assessments

Duration between the last response assessment and death or disease relapse

Table 17: Censoring Rules for Event-Free Survival (EFS)

No.	Situation	Event or Censoring Date	Outcome
If a patient achieved a CR at the analysis, the following rules (No. 1 to 6) will be applied.			
1	Disease relapse between scheduled visits	Date of the first assessment that determined disease relapse	Event
2	Death during the study with no prior disease relapse	Date of death	Event
3	Patients still on treatment without disease relapse as of data cut-off ^a	Date of the last response assessment ^b	Censored
4	Treatment discontinuation for reasons other than disease relapse or death	Date of the last response assessment	Censored
5	New anticancer treatment started	Date of the last response assessment before start of new treatment	Censored

No.	Situation	Event or Censoring Date	Outcome
6	Death or disease relapse after two or more missed response assessments ^c	Date of the last response assessment before start of new treatment	Censored
If a patient did not achieve a CR at the analysis, the following rules (No. 7 to 11) will be applied.			
7	Documented PD between scheduled visits	Date of the first assessment that determined PD	Event
8	Death during the study with no prior PD	Date of death	Event
9	Patients still on treatment without PD as of data cut-off ^a	Date of the last contact	Censored
10	Treatment discontinuation for reasons other than PD or death, and no post baseline response assessments	Date of the first dose	Censored
11	Treatment discontinuation for reasons other than PD or death with post baseline response assessments	Date of the last contact	Censored
12	New anticancer treatment started	Date of the last contact	Censored
13	Death or PD after two or more missed response assessments ^c	Date of the last contact	Censored
14	No baseline or unreadable baseline assessment but readable post baseline assessments	Date of the first dose	Censored

^a This refers to patients who were still receiving study treatment at time of data cutoff.

^b For EFS, the date of last response assessment refers to the date of last adequate response assessment.

^c Two or more missed response assessments is defined as having either one of the following two durations being longer than 126 days (= (28 [days/cycle] x 2 [cycles] + 7 [days]) x 2):

Duration between two consecutive response assessments

Duration between the last response assessment and death or disease relapse

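### SAP Tables 16 (RFS) and 17 (EFS): row 6 repeats row 5's censoring date, so a late relapse followed by new therapy is censored at the relapse visit itself

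*SAP*

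**What the plan says.** The SAP has a censoring table for each time-to-event endpoint. All but the OS table have a row for events that follow a long gap in assessments, defined in the footnotes as a gap of more than 126 days. The dates assigned in that row are:

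- Table 10 (PFS) row 7 and Table 12 (DOR) row 6: "Date of the last tumor assessment before missed assessments".
- Table 15 (duration of CR and of CR+CRi) row 6: "Date of the last response assessment before missed assessments".
- Table 16 (RFS) row 6 and Table 17 (EFS, patients with CR) row 6, for "Death or disease relapse after two or more missed response assessments": "Date of the last response assessment before start of new treatment". Row 5 of each table, which concerns patients who start new anticancer treatment, has the same words.
- Table 17 row 13 (EFS, patients without CR), for "Death or PD after two or more missed response assessments": the date of last contact.

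The outcome is censored in every case. The same tables also hold general rows that make death an event: "Death during the study with no prior disease relapse" (row 2 of Tables 16 and 17) and "Death during the study with no prior PD" (row 8 of Table 17). No order of precedence is stated. The second block of Table 17 opens with "If a patient did not achieve a CR at the analysis, the following rules (No. 7 to 11) will be applied", yet its rows run to 14.

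The RFS text in SAP 5.5.2.2 and in protocol 11.5.3.2.2 dates a death without reported relapse at the day of death, with no exception for missed assessments. SAP section 6 declares no changes to the planned analyses.

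**The concern.** Row 6 deals with missed assessments, and new treatment plays no part in the situation it describes. A date tied to new treatment therefore does not fit, and no reason is given for RFS and EFS to differ from PFS, DOR and duration of CR. The likely explanation is a cell pasted from the row above.

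At stake is whether RFS and EFS can be derived from the SAP as it stands, and whether they agree with duration of CR. Both RFS and duration of CR start at first CR, so one patient with one late relapse should not be censored at two dates months apart. A rule that the programmer must repair is also best repaired before anyone sees outcomes, and this study is open-label.

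**Working it through.** **Threshold.** From the table footnotes: (28 days × 2 cycles + 7 days) × 2 = 126 days, which reproduces the SAP's figure.

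**Row 6 against Table 15, case by case.** Assume the last adequate assessment before the gap is on study day 112, and that a visit at which relapse is found counts as a response assessment.

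| Late event | New treatment | Row 6, Tables 16 and 17 | Row 6, Table 15 |
|---|---|---|---|
| Death, no assessment after the gap | None | No date; obvious fallback is day 112 | Day 112 |
| Death, no assessment after the gap | Started during the gap | Day 112 | Day 112 |
| Relapse found on day 250 | Started on day 260 | Day 250 | Day 112 |
| Relapse found on day 250 | None | No date; no unique fallback | Day 112 |

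The two wordings part only when an assessment follows the gap, chiefly a late relapse visit.

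**One patient (assumed data).** CR on day 56, last assessed day 112, relapse found day 250, therapy from day 260. The gap is 250 − 112 = 138 days, above 126.

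- RFS by the text: event at 250 − 56 = 194 days.
- RFS by Table 16 row 6 as written: censored at 194 days.
- Duration of CR by Table 15 row 6: censored at 112 − 56 = 56 days.

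The two censored times differ by 194 − 56 = 138 days. Whenever row 6 lands on the relapse visit, this difference spans the qualifying gap, so it always exceeds 126 days (126 / 30.4375 = 4.1 months).

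**Effect on an estimate (assumed data).** Ten CR patients have RFS times of 60, 100, 120+, 150, 194, 200, 260+, 300, 340+ and 400+ days (+ means censored). The 194-day patient is the one above. Kaplan-Meier at day 200:

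- Counted as an event at 194: 9/10 × 8/9 × 6/7 × 5/6 × 4/5 = 0.457; median 200 days.
- Censored at 194 (row 6 as written): 9/10 × 8/9 × 6/7 × 4/5 = 0.549; median 300 days.
- Censored at 56 (Table 15 wording): 8/9 × 7/8 × 5/6 × 4/5 = 0.519; median 300 days.

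The copied date accounts only for the step between 0.549 and 0.519. The move away from 0.457, and the change in median, come from censoring late events at all.

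**Weight of one patient.** Protocol 11.1 gives 6 of 20 as the fewest complete responders whose interval excludes 10%, and the 50% target gives 10 of 20. One affected patient is then 1/10 = 10% to 1/6 = 17% of the RFS set.

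**Row 13 of Table 17.** Last contact can fall at or near a late death, and on or after a late PD visit. The patient is then carried as event-free up to or past the event, whereas the corrected row 6 would stop before the gap.

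**The case against.** The case for leaving this alone has real force. The other tables make the intended date plain. For a late death with no assessment after the gap, the fallback is unique and matches Table 15. A reader might infer that row 6 cannot be programmed at all; that goes too far, since the difficulty is confined to cases where an assessment follows the gap.

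A reader might also infer that the tables simply contradict the text and leave late events undefined. The documents do not support that either. The SAP text states the general definition and then refers to the table for censoring. Row 6 is a special case of rows 1 and 2, and row 13 of rows 7 and 8; only if the specific row prevails does each row have any effect. Protocol 11.4, 11.5 and 11.5.3 leave data handling and detailed methods to the SAP. Censoring after missed assessments is a recognised convention, used here for PFS, DOR and duration of CR as well.

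A third inference would be that patients assessed on schedule are caught, because marrow may be taken only every 6 months. The 126-day formula is built on the two-cycle imaging schedule. Which procedure counts as an adequate assessment in Cohort C is a separate question.

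Two things survive. The date in row 6 is wrong in both tables and gives a wrong result for a late relapse followed by therapy. And the protocol dates RFS deaths at death without exception, so censoring some of them is a departure that SAP section 6 does not record.

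**Conclusion.** Wrong as written. Row 6 of Tables 16 and 17 carries a date that belongs to row 5. It yields no date without new treatment, and where therapy follows a late relapse it censors RFS more than 126 days later than duration of CR in the same patient. This rests on the relapse visit counting as a response assessment.

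The consequence is limited. RFS covers complete responders only and EFS leukemia presentation only, within a cohort of about 20; both are secondary and estimation-only. The primary CR rate is unaffected. It would be tempting to claim a material bias in RFS or EFS from the copied date, but the documents do not allow it: the number of late relapses is unknown, and in the assumed set the date alone moved the day-200 estimate by 0.03 and left the median unchanged. Comparisons of late events counted against late events censored measure the missed-assessment convention, not this fault.

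The missing precedence statement and the undeclared departure from the protocol are real but minor drafting gaps.

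**What to change.** Before database lock:

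1. In row 6 of Tables 16 and 17, replace the date with the Table 15 wording, "Date of the last response assessment before missed assessments".
2. Correct the second subheading of Table 17 to cover No. 7 to 14, and reconcile row 13's last-contact date with the corrected row 6.
3. Add one sentence stating that the missed-assessment rows override the general event rows. Declare this in SAP section 6 as a departure from protocol 11.5.3.2.2, and report RFS and EFS with late events counted as events as a sensitivity analysis.

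The cost is two table cells, one subheading, the row 13 reconciliation, one precedence sentence, one declaration and one extra analysis of two endpoints. No new data are needed. RFS and EFS estimates may shift slightly if any patient falls under these rows.
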